13.3 Paper Case Report Forms (CRFs)

Paper case report forms are printable for data entry by the clinician for the patient. Paper forms are not required to be stored by the clinic following entry of the data electronically online.

13.4 Electronic Evaluation Forms (eCRFs)

All data forms are available on line for ease of data entry through click responses on PDF format forms with pull down menus to facilitate responses with helpful and prompting messages to guide you through the form and requested information. Once a form is saved the data is automatically updated same time for review by the responsible clinician.

Note: Please also refer to instructions online following access to the [REDACTED] interface has been provided to you by Cochlear.

13.5 Monitoring

There will be no routine on site monitoring of data entered. Participating clinics are not asked to store paper documents as source documents for data entered online; hence, no cross checks between data entered and source data is possible. Online spot-checks of recorded data to ensure quality assurance of data entered in terms of logic and ranges of data entered will be undertaken at random intervals and of randomly selected subsets of data during the course of the registry long-term. Data collected through observation of controlled market release of specific products may be subject to monitoring at regular intervals following prior agreement with the principal investigator for the defined period of the controlled market release. [REDACTED] for the Cochlear-IROS database, utilises an in-built audit trail for automated registration of all data entries and amendments by the authorised clinic personal and or patient.

13.6 Study Documents Online and Study Records

For convenience and ready access, all study documents are provided for viewing online upon access to the interface at any time after the chief investigator has signed the Registry Agreement online by all users in the clinic.

The study documents include:

1. Registry Plan
2. Registry Agreement Letter(s)
3. Patient Information Consent Form template.

Paper copies of the Registry records maintained by the clinic/centre and records will include:

- EC opinion/approval (as applicable for registry participation for the clinic)
- Individually signed Patient Informed Consent forms on Clinic letter head
- Clinic specific patient identification list/log of system automated confidential patient codes

Optional for paper records pending regional regulations include:

- Signed Registry Agreement (*E-signature recorded & stored electronically via the IROS interface upon first access by a collaborating clinic Chief investigator*)
- Signed Registry Plan
- Clinic specific patient identification list/log of system automated confidential patient codes
- Individual confidential EDC interface passwords for identification for multiple users at the same clinic.

The clinician is responsible to ensure all locally required paper study documents are stored for at least 5 years after the end of the study.

Electronic records of data entered on each evaluation tool per patient at each interval is stored in the centrally hosted database as mentioned in Section 13.2 of this Registry Plan. Clinics can access the raw data for each patient and patient groups entered for their clinic, at any time for download and storage onto local systems. Global data records are not available for local download.

13.7 Data Management

All international data shall be collected and collated over several years in an externally hosted electronic database with complete access to raw data provided to Cochlear AG in Basel and the Cochlear Technology Centre in Mechelen. All data shall be treated confidentially by Cochlear. The data management process for this clinical investigation is described in the related Data Management Plan. All electronic data shall be kept for a minimum period of **5 years** both in electronic format and on paper by the company Cochlear as per Good Clinical Practices.

All clinics will have access to the individual raw data and data summaries of registrations and progress for all patients in their care that is entered into the observational study at any time.

All requests for data reports and summaries shall be coordinated via the global project manager.

14 Reporting of Results

14.1 Investigator

Please refer to the *Registry Agreement Letter(s)* also available online under Documents. Confirmation of agreement to the conditions must be electronically submitted. This may also be printed out and filed on paper if desired by the clinic. Confirmation of having read and agreeing to the Registry Agreement is requested the first time the interface is accessed by a new collaborating clinic by the lead investigator

at the clinic. Once the lead investigator at the clinic has confirmed agreement electronically the interface will permit access to create the first patient at the clinic. If there is no agreement patient data may not be entered. The Registry Agreement states in brief that each clinic owns their own clinic data which is available for publication of statistically valid data at their own discretion. The investigator must also ensure each patient continues to receive routine clinical treatment and care, irrespective of participation in the registry. Cochlear owns and has access to global data entered into the e-platform for the registry and intends to use it as appropriate for non-peer reviewed reports to support decision makers across regions.

14.2 Sponsor

Cochlear, the sponsor will use this data to provide statistically valid data to support patient management decisions at the clinical, administrative, marketing, reimbursement and regulatory levels locally, nationally and internationally. Reports are to be developed at regular intervals back to the contributing clinics and at request of the relevant health and government bodies. Established benefits will be used to support benefit claims from use of bilateral stimulation over unilateral stimulation for scientific, regulatory and market oriented communications.

The study obligations for the Sponsor and the investigator are followed as outlined in guidelines for ISO14155 and the Declaration of Helsinki. These will be reviewed with the clinician prior to the start of the registry at initiation visit.

15 Withdrawal of Sponsor

Following written communication to notify in advance all participating collaborating clinics, the sponsor may elect to withdraw sponsorship of the registry if,

- patient recruitment rate is not growing sufficiently over time to warrant the support of resources involved..
- there is no willingness to collaborate in the registry by the clinicians on the whole.

Note: In the event the registry is closed, patients enrolled to this date would be permitted to complete evaluation to 2 years post-implant

16 Overview of Case Report Forms and Questionnaires available online

Baseline evaluation

By the patient
 Implant Recipient Baseline
 HUI Mark III questionnaire
 Speech Spatial Qualities questionnaire
By the Clinician

Clinician Baseline (compulsory)
Unaided Hearing threshold summary- pre-implant
Unaided Hearing thresholds - immediately post implant
End of study form (if needed)
Product specific forms

1st year follow up

By the patient
Implant Recipient follow-up
HUI Mark III questionnaire
Speech Spatial Qualities questionnaire
By the Clinician
Annual Follow-Up Clinician Yr 1 (compulsory)
Unaided Hearing Thresholds - Yr 1
End of study form (as needed)
Product specific forms

2nd year follow up

By the patient
Implant Recipient follow-up form
HUI Mark III questionnaire
Speech Spatial Qualities questionnaire
By the Clinician
Annual Follow-Up Clinician Yr 2 (compulsory)
Unaided Hearing Thresholds -Yr 2
End of study form (as needed)
Product specific forms

3rd year follow up (optional)

By the patient
Implant Recipient follow-up form
HUI Mark III questionnaire
Speech Spatial Qualities questionnaire
By the Clinician
Annual Follow-Up Clinician -Yr 3 (compulsory)
End of study form (compulsory)
Product specific forms

## INTRODUCTION

This document is a companion document to the Clinical Investigation Plan CEL5277 but does not replace any previous statistical analysis plan: It is to describe the intended method of analysis of data in the adult IROS database with the aim to produce four publications.

It includes a comprehensive description of the recorded sample sizes, the intended statistical analyses with reference to the primary and secondary hypotheses, and additional statistical considerations such as the treatment of missing data.

There is no need to report deviations from this statistical analysis plan in any reports relating from the IROS data source.

The planned analysis for each publication is described in separate sections.

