## 1 REAL LIFE OUTCOMES VERSUS AGE FOR CI

### 1.1 Overall objectives

- Clinical Evidence Strategy: Healthy Aging
- Pivotal Hypothesis: Are there differences in outcomes with CI for different age ranges, and impact on subject's life
- Primary measures: HUI3, SSQ (complete scales)
- Secondary measures: Changes in HUI3 >0.03, changes in SSQ >2 (i.e. dichotomisation of outcomes), changes in employment status pre and post (1 year, and sustained at 2 years), Medical leave after surgery, employment and other specific questions and listening effort (e.g. from SSQ).
- Age groupings for comparisons:
  - Use ABS-type age groupings 18-34, 35-44, 45-54, 55-64, 65+
  - Note that the younger age groups were combined due to sample size.
- Descriptive statistics of sub populations/ predictors (to be compared: pre and post, pre vs post, by age group, and as potential predictors in regression analyses)
  - Onset of deafness
  - Etiology
  - Hearing loss degree
  - HA use/presence (in the implanted ear at baseline and contralateral ear at baseline and visit 1)
  - Telephone use
  - Presence of tinnitus
  - Presence of dizziness
  - Employment status
  - Whether hearing ability negatively affected work
  - Has ability to do job changed post implant
  - Medical leave (taken and amount)
- Considerations:
  - Bilateral implant summaries were also of interest but were not possible due to small numbers.
  - Some of the above summaries may not be possible due to (subgroup) sample sizes.
  - The questions around employment and leave may not have been captured in a usable form, as such these variables will be explored more carefully, and analyses should be interpreted cautiously.

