#### **1.3.3.2 Per Protocol dataset**

These are observational, retrospective data and therefore per protocol is not well defined. As above, the data will be examined to determine whether characteristics are different between those who are present or absent at the various follow-up time points.

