### **1.3.7 Presentation of data**

The report will conform to a conventional format with a number of data completeness and population summaries (such as demographics).

For the age groupings, ABS age ranges will be utilised unless sample sizes are too small. In this situation, one or more groups will be combined. While quintiles were of interest the age breakpoints were not useful and not considered further.

For all linear and linear mixed-effects models, estimates of the marginal means and plots of change over time will be presented. P-values for interaction effects and differences between groups (where relevant because of significance or interaction or main effects) will be presented. For logistic models estimated odds ratios and p-values will be presented.

Tables of summaries at each time point will be presented for the overall cohort as well as for those present or absent at a subsequent time point. Tables of cross-tabulations will also be presented.

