## 4.1 Statistics

### 4.1.1 Sample Size

The decision of success/fail in significant impact of CI on HUI3 scores requires paired pre/post data in order to test the difference scores. Currently one centre has good follow-up, ZA-01, and overall a high number of patients with 161 at baseline and 117 at 1 year as of December 2019. Thus approximately 110 datapoints are available.

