#### 4.1.2.1 Pass/Fail Criteria

[figure not shown]
The minimum clinically important change/difference in HUI3 is 0.03 units. For HUI3 this change is very small and larger mean differences are typically observed. As such for these analyses we are interested in differences/changes of at least 0.1 units. Below is summarised the simple paired comparison of baseline versus 1-year HUI3 scores:

```
> t.test(dat.w.temp$hui.v3.score.multi.1,dat.w.temp$hui.v3.score.multi.0, p
aired=TRUE)
```

```
Paired t-test
```

```
data: dat.w.temp$hui.v3.score.multi.1 and dat.w.temp$hui.v3.score.multi.0
t = 5.9659, df = 132, p-value = 2.105e-08
alternative hypothesis: true difference in means is not equal to 0
95 percent confidence interval:
 0.09963182 0.19847490
sample estimates:
mean of the differences
      0.1490534
```

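### The SAP waives reporting of deviations in any IROS report although Section 4 was written with HUI3 outcomes already seen, so reports need not flag departures from the plan or choices made after results were known

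*SAP*

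**What the plan says.** The SAP Introduction sets the document's purpose as describing the "intended method of analysis of data in the adult IROS database with the aim to produce four publications". It then adds: "There is no need to report deviations from this statistical analysis plan in any reports relating from the IROS data source".

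On the state of the data when the plan was written:

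- Section 1.3.3.2: "These are observational, retrospective data and therefore per protocol is not well defined".
- Section 1.1, on age bands: "Note that the younger age groups were combined due to sample size". Section 1.3.7, on an alternative grouping: "While quintiles were of interest the age breakpoints were not useful and not considered further".
- Section 4.1.2.1 prints R output comparing HUI3 at 1 year with baseline: "t = 5.9659, df = 132, p-value = 2.105e-08". It then reads a histogram of individual gains as showing that somewhat more than half of cases exceed 0.1.
- Section 4.1.2.3 prints a cross-table of the HUI3 hearing attribute at baseline and visit 1.

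On choices left open:

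- Sections 4.1.2.1 and 4.1.5 allow the success cut-off to be varied after initial results, to improve prediction.
- Section 4.1.2.2 compares patients who meet the criterion with those who do not, and then forms hypotheses from the characteristics that differ.
- Section 1.3.7 covers age bands that prove too small: "In this situation, one or more groups will be combined".
- Section 1.3.3.1 leaves the last time point as possibly year 2 or year 3.

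On dates, Section 7 logs one version, dated 5 Nov 2019, while Section 4.1.1 gives one centre's counts as "161 at baseline and 117 at 1 year as of December 2019".

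**The concern.** A SAP lets a reader separate tests fixed in advance from those chosen once results were known. Plans for data already collected are common and acceptable, but they then depend on disclosure: what had been seen, what was still open, and what changed. This SAP states the opposite rule. It does not merely omit a deviations section; it says that none is needed in any report from this source.

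At stake are the odds ratios and p-values of the two inferential publications, on age (Section 1) and on predictors of HUI3 gain (Section 4). Protocol 14.2 describes wide use of registry results, including reimbursement and regulatory decisions. Protocol 14.1 says the sponsor intends to use the global data in reports that are not peer reviewed, so peer review would not supply the missing check there.

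**Working it through.** **1. Does anything restore the duty?** The nearest provisions are these:

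- SAP 1.3.5 and 4.1.3: software versions are noted.
- SAP 1.3.6 and 4.1.4: quality control of code and summarised data.
- SAP 1.3.7 and 4.1.5: what will be presented.
- Protocol 13.5: an audit trail of data entries.

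None of them records departures from the analysis plan.

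**2. Had outcomes been seen?** The printed t-test can be reproduced from its own figures.

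- SE = mean / t = 0.1490534 / 5.9659 = 0.02498.
- 95% CI = 0.14905 ± t(0.975; 132) × 0.02498 = 0.0996 to 0.1985, as printed.
- Two-sided p = 2.10 × 10⁻⁸, as printed.
- Pairs = df + 1 = 133. Implied SD of change = 0.02498 × √133 = 0.288.
- Rows of the hearing-attribute table: 37 + 47 + 2 + 40 + 2 + 5 = 133.

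Paired outcome data on 133 patients had therefore been analysed for Section 4. The evidence differs by section:

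| SAP section | Outcomes shown | Formal tests planned |
|---|---|---|
| 1 (age) | Small pre/post sample, not by age group; no IROS age-by-visit result | Yes |
| 2 (device choice) | None | No (2.3.2) |
| 3 and 5 | Not currently applicable | None |
| 4 (factors) | t-test, gain histogram, baseline-by-visit-1 table | Yes |

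**3. Which open choices depend on outcomes?**

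| Choice | Section | Depends on |
|---|---|---|
| Merging age bands | 1.3.7 | Group sizes |
| Year 2 or 3 as last time point | 1.3.3.1 | Amount of follow-up |
| HUI3 cut-off | 4.1.2.1, 4.1.5 | Model results |
| Predictors to hypothesise | 4.1.2.2 | Observed differences between responders and non-responders |

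All four are written into the plan, so using them is not a deviation. The last two depend on outcomes. A rule confined to deviations would miss them, so the fix must also cover which permitted option was used.

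**4. Illustration of size.** The documents do not say how many options will be tried, so this rests on assumptions and does not estimate the error in the publications. Gains were simulated as normal with mean 0.149 and SD 0.288, with predictors unrelated to gain, n = 110 or 133, and 4,000 runs each. False-positive rate for one predictor at nominal 5%:

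- Cut-off fixed at 0.1: about 5%.
- Smallest p over 0.03, 0.1 and the median (all mentioned in Section 4): 9% to 10%.
- Smallest p over seven cut-offs (those three plus an assumed 0.05, 0.15, 0.2 and 0.25): about 14%.

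This is an adverse case. The SAP speaks of tuning for predictive performance, not of choosing the smallest p-value.

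**5. Dates and counts.** A document whose only logged version is dated 5 Nov 2019 quotes counts from the following month. Section 4.1.1 expects about 110 pairs from a centre with 117 patients at 1 year, whereas the t-test and table hold 133. A figure in 4.1.2.3 is described as covering all CI subjects, so the t-test population may be wider than that centre. The SAP does not say.

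**The case against.** The strongest reply is that the sentence removes a need to report and does not forbid reporting. The SAP states its hypotheses and models for Section 1 (1.3.2.2, 1.3.2.3), its additional tests (1.3.4.4) and what will be presented (1.3.7, 4.1.5). A reader might infer that planned and post hoc results cannot be told apart at all. That goes too far, because anyone holding the SAP can compare it with a report. What stands is that the report need not flag a change, and that the permissive wording of Section 4 gives the reader little to compare against.

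Other stronger readings are also unsupported:

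- *The whole SAP was written after outcomes were analysed.* The evidence is confined to Section 4. Calling the data retrospective in Section 1.3.3.2 does not show that age-by-visit results had been seen.
- *Age merging and the year 2 or 3 choice are undisclosed deviations.* Both are stated options that depend on counts or follow-up.
- *The 0.1 cut-off was taken from the data.* Section 1.3.1 also names 0.1, on the ground that 0.03 is very small. The histogram supports the choice but is not its only basis.
- *The SAP was edited after 5 Nov 2019 without being logged.* A wrong date in either place would explain the mismatch equally well, and the SAP's front pages were not available for this review.
- *The 5% level has no meaning.* Undisclosed selection weakens it by an unknown amount. Within the SAP, 5% appears only in the sample-size calculations.

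Scope also limits the point. The SAP is a companion document that replaces no previous analysis plan, and the waiver covers deviations from this SAP only. The one benefit claim named in Protocol 14.2, bilateral over unilateral stimulation, is not tested here; SAP 1.1 says bilateral summaries were not possible. The sentence might have been meant only for other IROS reports, but its wording covers any report and would still need correcting.

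**Conclusion.** The concern holds in a limited form. The SAP expressly waives deviation reporting, no other provision restores it, and Section 4 was written with HUI3 outcomes seen while leaving outcome-dependent choices open. Reports on Sections 1 and 4 therefore need not reveal which results departed from the plan or were chosen after outcomes were known, and their p-values can support less than a reader would assume. The effect is clearest for Section 4, weaker for Section 1, and slight for Section 2.

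The inflation cannot be quantified from the documents. The range of about 5% to 14% per predictor depends on the assumed distribution and on selecting the smallest p-value. The date mismatch is a separate version-control point and shows only that the two dates must be reconciled. This should be fixed; the waiver by itself invalidates no stated estimate, sample size or test.

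**What to change.** Delete the waiver in the SAP Introduction and replace it with a requirement that each report:

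- lists every deviation from the SAP, with the reason and whether it was decided before or after the relevant outcomes were seen;
- labels analyses that are not in the SAP as post hoc;
- states which pre-specified option was used (HUI3 cut-off, age grouping, last time point), and labels as exploratory any option chosen after seeing outcomes.

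Separately, reconcile the version date in Section 7 with the December 2019 counts in Section 4.1.1. Record there the data-cut date and which sections were written after HUI3 or SSQ results had been seen. State which patients make up the 133 pairs.

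The cost is a few sentences of SAP text, a corrected change history and a short deviations table in each report. No new data or analysis is needed.

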## 1 REAL LIFE OUTCOMES VERSUS AGE FOR CI

### 1.1 Overall objectives

- Clinical Evidence Strategy: Healthy Aging
- Pivotal Hypothesis: Are there differences in outcomes with CI for different age ranges, and impact on subject's life
- Primary measures: HUI3, SSQ (complete scales)
- Secondary measures: Changes in HUI3 >0.03, changes in SSQ >2 (i.e. dichotomisation of outcomes), changes in employment status pre and post (1 year, and sustained at 2 years), Medical leave after surgery, employment and other specific questions and listening effort (e.g. from SSQ).
- Age groupings for comparisons:
  - Use ABS-type age groupings 18-34, 35-44, 45-54, 55-64, 65+
  - Note that the younger age groups were combined due to sample size.
- Descriptive statistics of sub populations/ predictors (to be compared: pre and post, pre vs post, by age group, and as potential predictors in regression analyses)
  - Onset of deafness
  - Etiology
  - Hearing loss degree
  - HA use/presence (in the implanted ear at baseline and contralateral ear at baseline and visit 1)
  - Telephone use
  - Presence of tinnitus
  - Presence of dizziness
  - Employment status
  - Whether hearing ability negatively affected work
  - Has ability to do job changed post implant
  - Medical leave (taken and amount)
- Considerations:
  - Bilateral implant summaries were also of interest but were not possible due to small numbers.
  - Some of the above summaries may not be possible due to (subgroup) sample sizes.
  - The questions around employment and leave may not have been captured in a usable form, as such these variables will be explored more carefully, and analyses should be interpreted cautiously.

